Full Study Title: Effect of a Wide Spectrum Nutritional Supplement on Mitochondrial Function in Children with Autism Spectrum Disorder (ASD)

Principal Investigator: [name]; Co-Investigators: [name]

Sponsor: [name]; IND 142751; ClinicalTrials.gov ID: NCT03835117; Protocol Version 02/11/2022

Funding Source: Turnabout for Autism (Private Foundation), Pleasanton CA.

	Synopsis
Protocol Title	Effect of a Wide Spectrum Nutritional Supplement on Mitochondrial Function in Children with Autism Spectrum Disorder (ASD)
IRB	WCG Institutional Review Board
Protocol Ver	Wednesday, August 3, 2022
Sponsor	[name], Rossignol Medical Center, Phoenix AZ
IND # / FDA	IND 142751; FDA Division of Psychiatry; Protocol Version 1.4
NCT ID	NCT03835117
Principal Investigator	[name], PhD, Rossignol Medical Center, [name]
Site- Investigator	[name], Southwestern Autism Resource and Research Center (SARRC), Phoenix AZ
Co-Investigators	1. [name], Director of CNNH NeuroGenomics Program, Center for Neurological and Neurodevelopment Health, Voorhees, NJ. 2. [name] D.O. (SARRC), Phoenix AZ
Clinical Sites	1. SARRC, Phoenix, AZ
Laboratory Sites	1. Laboratory of [name], State University of New York Downstate—[name] 2. Religen Inc, Plymouth Meeting, PA 3. Laboratory of [name], Icahn School of Medicine at Mount Sinai, NY NY 4. Laboratory of [name] at the University of Oklahoma Health Sciences Center in Oklahoma City, OK 5. 3billion Laboratory in Seoul, South Korea 6. Iliad Inc, Plymouth Meeting, PA
Study Design	Prospective Randomized 24-week Double-Blind Placebo-Controlled Cross-over
Objectives	To evaluate the metabolic effects of a comprehensive wide-spectrum supplement for children with ASD to determine whether it physiologically targets mitochondrial pathways known to be abnormal in children with ASD.
Participants	Up to 50 children, aged 2 years 6 months to 17 years 3 months with confirmed ASD and mitochondrial dysfunction. Participants will have moderate disease severity (clinic global impression of 4 or above) and stable behavioral, education and medical treatment. Those with severe intellectual impairment, disruptive behavior or medical conditions such as epilepsy will be excluded.
Investigational Product	Weight adjusted wide-spectrum oral nutritional supplement powder and gel capsules that targets mitochondrial support produced by NeuroNeeds (Old Lyme, CT) taken in two divided doses vs oral placebos.
Safety	Physical examination, safety labs, Adverse Event Reporting, safety monitoring
Statistical Methods	The primary analysis will be intent-to-treat, defined as all randomized subjects. Mixed-model regression will determine whether blinded treatment produces a greater normalization in mitochondrial function over the 12-week period as compared to placebo treatment over the same time period. Similar analysis will test secondary outcome measures. Assuming a medium effect size of 0.5, the study provides an 80% power assuming a 0.01 alpha (allowing correction for multiple primary end-points). Secondary outcome measures will include the Improvement item of the Clinical Global Impression Scale and behavioral scales such as the Aberrant Behavior Checklist. Multivariable logistic regression will be used to select biomarkers that can significantly predict treatment response.

Full Study Title: Effect of a Wide Spectrum Nutritional Supplement on Mitochondrial Function in Children with Autism Spectrum Disorder (ASD)

Principal Investigator: [name]; Co-Investigators: [name]

Sponsor: [name]; IND 142751; ClinicalTrials.gov ID: NCT03835117; Protocol Version 02/11/2022

Funding Source: Turnabout for Autism (Private Foundation), Pleasanton CA.

Funding	Turnabout for Autism (Private Foundation), Pleasanton CA
---------	--

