## 5. RESEARCH PLAN

### Trial Design

50 children with ASD and signs and symptoms of abnormal mitochondrial activity will be randomized in 1:1 ratio to receive a wide-spectrum nutritional supplement that targets mitochondrial function or placebo for 12 weeks under DBPC conditions. Each participant will serve as their own control in the cross-over design. Using a phone screen, we will identify children (age  $\geq$  2:6 and  $<$  17:3) with a diagnosis of ASD and evidence of mitochondrial function which is significantly higher or lower than average (here forth referred to as mitochondrial dysfunction). Children with suspicion of mitochondrial dysfunction will be invited to participate in a screening visit to make sure they meet including and exclusion criteria. If the screening visit is longer than 6 weeks from the prescreening, we will repeat the baseline metabolic testing to ensure an accurate baseline mitochondrial measurement. If they meet criteria, the baseline visit will be completed within 2 week but we will attempt to complete it on the same day (Table 1). Upon successful completion of the baseline visit, the participant will enter Phase 1 of the trial and will be randomized to receive active treatment or placebo for 12 weeks under DBPC conditions. At the end of the 12 weeks (end of Phase 1), the participant will return for evaluations similar to the ones conducted at baseline. Upon successful completion of the post-Phase 1 visit, the participant will start Phase 2 where they will receive active treatment or placebo, depending on what they received during Phase 1 – they will be crossed over to the opposite treatment regimen. Potential AEs, compliance and concomitant treatments will be monitored every four weeks.

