## **Laboratory Assessments**

7. **Safety laboratories**: Safety labs will be measured at the screening visit. These will include a complete blood count and a comprehensive metabolic panel.
8. **Biomarker**: Most biomarkers will be collected at baseline and after each treatment arm to determine if the treatment results in a change in these biomarkers. Baseline biomarkers will help understand whether treatment response can be predicted from biomarker tests.
  - a. Buccal swabs will be collected to assess mitochondrial function.
  - b. Plasma, Peripheral Blood Mononuclear Cells (PBMCs), DNA, and RNA will be collected and stored locally for future analysis, such as oxidative and methylation metabolism, bioenergetics, immune biomarkers, gene expression, epigenetics, and gene sequencing. 3billion Laboratory in Seoul, South Korea will perform genetic sequencing to look for causative mutations if good quality DNA is obtained and can be isolated. Samples will be stored until they are used up or destroyed, when possible. The PI, [name], will retain control over the blood sample unless it is requested that the sample be destroyed and then it will not be used for any future studies. If the participant wishes to have the sample removed from storage and destroyed at any time, they may contact a study coordinator or PI. IRB permission will be obtained prior to sharing samples for future studies. These samples will be de-identified and no protected health information will be shared with collaborators. If samples are shared, a log of those who withdraw samples will be documented thoroughly.
  - c. Deciduous teeth and hair samples will also be collected and sent to [name] laboratory. Recent research suggests prenatal nutritional metal concentrations measured in deciduous teeth correlate with long-term language development and may predict treatment response and other recent studies support the measurement of unique metabolic markers using hair samples.
  - d. Folate receptor  $\alpha$  autoantibody (FRAA) titers will be sent to the laboratory of [name], Ph.D. at the State University of New York, Downstate (Brooklyn, NY) or Iliad Neurosciences. We have demonstrated in one study that FRAA are related to methyl-B12 metabolism.

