## **Statistical Analysis**

All data analysis for the primary study aims will be conducted by the principal investigator. The primary analysis will be intent-to-treat, defined as all randomized subjects. Exploratory “per protocol” analysis will be conducted on participants who adhered to protocol. Analyses will be performed with R 3.02 (<http://www.r-project.org>) or SAS 9.3 (SAS Institute, Cary, NC).

Sample Size Justification and Power Analysis: Assuming a medium effect size of 0.5, the study provides an 80% power assuming a 0.01 alpha (allowing correction for multiple primary end-points)..

Primary Hypothesis: After 12 weeks of taking the nutritional supplement will improve mitochondrial function more than taking the placebo for 12 weeks. To test this hypothesis, we will use a mixed model using baseline and all post-randomization measures of mitochondrial activity. To deal with missing post-treatment data, the model will be conditioned on all baseline values. This conditional joint response model is more tolerant of missing data than ANCOVA and is less biased than carrying baseline data forward to endpoint.

Safety analyses: Adverse events (AE) will be systematically monitored using a 34-item form. It includes specific queries about major body systems, activity level, sleep, appetite, and general health. New events, whether presumed related to treatment or not, are classified as AEs and rated as Mild, Moderate or Severe (see details below). The occurrence of an AE will be counted once at the highest level of severity (e.g., a report of mild nausea followed by a report of moderate nausea in the same child would count as an occurrence of moderate nausea). The frequency of AEs by severity will be evaluated using a Fisher’s exact test. We will pursue exploratory analyses such as survival analyses using time to AE as the response variable.

Validation of the CGI-ASD: In addition to the standard CGI-S and CGI-I we will use a new a structured CGI rating scale called the CGI-S-ASD and CGI-I-ASD respectively. We will compare the performance of the standard and new CGI rating scales. Since the CGI-ASD provide guidance for completing the ratings we will have the rater complete the standard scale before the new scale. The correspondence between each scale and other outcome measures will be studied as well as the performance of the scales as outcome measures.

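### The only multiplicity provision is a fixed 0.01 alpha in the power sentence; for a family of two to five primary end-points, Holm's step-down test at 0.05 would never reject less and can reject more

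*Combined protocol and SAP*

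**What the plan says.** The Synopsis (Statistical Methods) and section 6 (Statistical Analysis, Sample Size Justification and Power Analysis) carry the same sentence. It opens "Assuming a medium effect size of 0.5" and continues "the study provides an 80% power assuming a 0.01 alpha (allowing correction for multiple primary end-points", where the parenthesis closes. The sample size comes from section 5, Trial Design: "50 children with ASD and signs and symptoms of abnormal mitochondrial activity will be randomized in 1:1 ratio". The Synopsis makes 50 a ceiling.

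Nothing else in the plan deals with multiplicity. No correction method, familywise level, sidedness or count of primary end-points is given. The analysis text in section 6 describes a mixed model for one primary hypothesis, on mitochondrial function, and sets no significance threshold.

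The family itself is unsettled. Section 4 places mitochondrial activity and redox metabolism under the Primary Aim. Section 5, item 15 calls the CGI-I a key primary outcome, while the Synopsis lists it as secondary.

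**The concern.** A reader who has to apply a correction from this text has one number to work with, 0.01, and the natural use is to hold every primary end-point to it. For five end-points that is Bonferroni at 0.05. For two to four it spends less than 5% of familywise error. In either case a step-down rule gives 5% control under any correlation and can claim more.

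Power is scarce here. The sample is at most 50 children, no dropout allowance is stated, and 80% is the planned power per end-point. A supplement aimed at mitochondrial function could plausibly move several related measures, which is the situation where a single-step rule loses most. Section 6 also assigns the primary analysis to the principal investigator, so the decision rule should be fixed in writing beforehand.

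**Working it through.** **Inputs.** From the plan: n = 50, standardised effect d = 0.5, alpha 0.01, power 80%, two-period cross-over. Assumed, because the plan is silent: d is on the SD of the within-child difference, tests are two-sided, all 50 children give complete pairs, the familywise level is 0.05, and the family has m end-points.

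**Reproducing the 80%.** Paired t-test, 49 df, noncentrality d√n = 0.5 × √50 = 3.54. Power at two-sided 0.01 is 79.9% (also 79.9% with the 48 df of a two-period cross-over). The plan's figure is reproduced. At other thresholds:

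- 0.0125: 82.2%
- 0.0167: 85.0%
- 0.025: 88.5%
- 0.05: 93.4%

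**What a flat 0.01 spends.** By Bonferroni's inequality, familywise error is at most 0.01 × m: 0.02 for two end-points, 0.03 for three, 0.04 for four, 0.05 for five. For six the bound is 0.06, and with independent tests the error is 1 − 0.99⁶ = 5.9%. So 0.01 guarantees 5% only up to m = 5.

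**Why Holm cannot reject less when m ≤ 5.** Holm compares the j-th smallest p-value with 0.05/(m − j + 1) and stops at the first failure. The smallest of these thresholds is 0.05/m, which is at least 0.01 when m ≤ 5. Every p-value at or below 0.01 therefore passes. The sequences are:

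- m = 2: 0.025, 0.05
- m = 3: 0.0167, 0.025, 0.05
- m = 5: 0.01, 0.0125, 0.0167, 0.025, 0.05

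**Size of the gain.** Simulated paired t-tests, n = 50, d = 0.5 for affected end-points, equal correlation 0 to 0.6 between end-points, 40,000 trials per setting. Entries are power per affected end-point.

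| End-points | Affected | Flat 0.01 | Bonferroni 0.05/m | Holm at 0.05 |
|---|---|---|---|---|
| 2 | 2 | 80% | 89% | 92–93% |
| 2 | 1 | 80% | 89% | 89% |
| 3 | 3 | 80% | 85% | 90–92% |
| 3 | 2 | 80% | 85% | 87–88% |
| 3 | 1 | 80% | 85% | 85% |
| 5 | 5 | 80% | 80% | 88–91% |
| 5 | 3 | 80% | 80% | 83–84% |
| 5 | 2 | 80% | 80% | 82% |
| 5 | 1 | 80% | 80% | 80% |

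For two or three end-points, part of the gain comes from using the full 5% and only the rest from stepping down. For five, all of it comes from stepping down. Holm's familywise error was at or below 5% within simulation error.

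The chance of winning at least one end-point is the same under both rules when m = 5, because the first Holm step is also 0.01. With two end-points, both affected and correlated 0.5, it rises from 91% to 96%.

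The gain shrinks as correlation rises. With five of five affected, Holm gives 91% at correlation 0, 88% at 0.6 and 87% at 0.8.

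**Above five.** With m = 8, Holm starts at 0.05/8 = 0.00625, where power is 74.7%. The flat rule has more power there, but only because its familywise error can reach 1 − 0.99⁸ = 7.7% with independent tests.

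**The case against.** The strongest objection is that the flat rule is not in the plan. The 0.01 is an alpha assumed for the power calculation, and "allowing correction for multiple primary end-points" can mean only that room was left for a correction to be chosen later. Holm is compatible with that sentence, since with five end-points its first step is 0.01. This stands. A reader might infer that the plan tests every primary end-point at 0.01, but the text does not say so, and the point is conditional on that use. It still calls for action: if 0.01 is the rule, a better one is available for two to five end-points; if no rule was fixed, one is needed.

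Other limits also stand:

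- With one primary end-point, as the section 6 hypothesis could be read, no correction is needed and Holm is irrelevant. Power at two-sided 0.05 would be 93.4%.
- A reader might infer that any second or third result with p between 0.01 and 0.05 could be claimed. It could not. With five end-points the second-ranked p must be at or below 0.0125 and the third at or below 0.0167; only the last may reach 0.05.
- Item 8a of the Laboratory Assessments says "Buccal swabs will be collected to assess mitochondrial function", and a reader might take shared sampling as a reason to expect a larger gain. Correlation reduces the gain.
- A single-step rule has a return: simple simultaneous 99% intervals, and a decision on each end-point that does not depend on the others.

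**Conclusion.** The point holds in conditional form. For a family of two to five, Holm at a two-sided familywise 0.05 never rejects less than a flat 0.01. Per-end-point power rises from 80% to about 88–93% when all end-points respond. With five end-points the gain is about 2 points if two respond and nil if one does.

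These sizes rest on 50 complete pairs, continuous end-points and d = 0.5 on the within-child difference scale, which the plan does not specify. With completers only, an assumed 10% or 20% loss lowers the starting 80% to 74% or 67%. Holm itself needs only valid p-values, so it also applies if CGI-I response joins the family, though the sizes above would not carry over to it.

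The documents do not support the stronger reading that the plan is in error. A flat 0.01 is valid for up to five end-points, merely conservative. Nor do they support a claim that Holm is better for any family size: above five, a flat 0.01 does not guarantee 5%, and a valid rule must start lower.

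**What to change.** In the Synopsis (Statistical Methods) and section 6 (Statistical Analysis), list the primary end-points by name, deciding whether redox metabolism (section 4) and CGI-I (section 5, item 15) belong. Then add: the listed primary end-points are tested by Holm's step-down procedure at a two-sided familywise alpha of 0.05.

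Keep 80% at 0.01 as the minimum power per end-point, described as valid for families of up to five. If the list exceeds five, recompute power at 0.05/m. If it contains one end-point, state a two-sided 0.05 and drop the correction.

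The cost is the list and one sentence, with no extra children, visits or data. The downside is that confidence intervals matching Holm decisions are less simple than flat 99% intervals.

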#### **4. SPECIFIC AIMS**

**Primary Aim: To determine if a wide-spectrum nutritional supplement can influence**

**mitochondrial activity in 50 individuals with ASD and signs and symptoms of abnormal**

**mitochondrial function.** The trial design will be a 24-week randomized, DBPC cross-over study.

We hypothesize that the supplement will result in a greater ability to normalize mitochondrial activity as compared to placebo. To test this hypothesis we will:

- a. Test mitochondrial activity at baseline and after the placebo and supplement arms of the study and determine if the nutritional supplement normalizes mitochondrial activity significantly more than placebo.
- b. Test redox metabolism at baseline and after the placebo and supplement arms of the study and determine if the nutritional supplement improves redox metabolism significantly more than placebo.
- c. To determine if specific biomarkers (Folate Receptor Autoantibody, Single Nucleotide Polymorphism) can predict response to treatment.

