  - e. Saliva will be collected from the participant and biological parents to investigate whether single nucleotide polymorphism (SNPs). Parental SNPs are important to understanding whether the SNPs in the children are significant or not – for example, if parents have the same SNP profile as the child, the SNP is unlikely to have a significant effect of pathophysiology.
  - f. Autoantibodies to neuronal tissue may be assessed by the Laboratory of [name] at the University of Oklahoma Health Sciences Center in Oklahoma City, OK if enough sample is available for the assay.

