Extra Sample Collection: As an optional portion to the research, deciduous teeth and hair samples can also be collected and sent to [name] laboratory. Recent research suggests prenatal nutritional metal concentrations measured in deciduous teeth correlate with long-term language development and may predict response to various treatments and other recent studies support the measurement of unique metabolic markers using hair samples.

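### Biomarkers are to be selected by significance in at most 50 children with no stated candidate number, alpha or correction; at 0.05 the chance of a false predictor is about 7–13% with 2 candidates and 61–71% with 20

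*Combined protocol and SAP*

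**What the plan says.** The method is one sentence in the synopsis, under Statistical Methods: "Multivariable logistic regression will be used to select biomarkers that can significantly predict treatment response". The Statistical Analysis text in Section 6 covers the primary hypothesis, safety and the CGI-ASD comparison, and does not mention this model.

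The aim it serves is item c of the Primary Aim in Section 4: "To determine if specific biomarkers (Folate Receptor Autoantibody, Single Nucleotide Polymorphism) can predict response to treatment". That names two types of marker and no number of SNPs. Section 5, Laboratory Assessments, item 8 is wider: "Baseline biomarkers will help understand whether treatment response can be predicted from biomarker tests". Section 6 adds, for deciduous teeth, that metal concentrations "may predict response to various treatments".

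Other text narrows the pool. The Tertiary Aim defers expression, methylation, sequencing and protein work until there is funding, and lists folate receptor autoantibodies among the deferred assays. Teeth and hair are optional in Section 6. Neuronal autoantibodies depend on there being enough sample.

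The synopsis sets the size: "Up to 50 children, aged 2 years 6 months to 17 years 3 months". The only alpha is in the power statement: "Assuming a medium effect size of 0.5, the study provides an 80% power assuming a 0.01 alpha (allowing correction for multiple primary end-points". The only binary response rule is a CGI-I rating of Much or Very Much Improved (Section 5, item 15), and it is not linked to the biomarker model.

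**The concern.** Picking predictors because they are significant, and then reporting them from the same children, has two known effects. The chance that at least one useless marker is kept grows with the number tried, and the model that is kept looks better than it is. Both are worst when events are few. The cross-over does not help. Although "Each participant will serve as their own control in the cross-over design", a baseline marker varies only between children, so there are at most 50 independent marker profiles.

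Aim c stands under the Primary Aim and is not labelled exploratory. Section 7 offers, in hedged terms, the prospect of identifying subgroups who could benefit. A chance marker with an apparent AUC above 0.7 would look like such a subgroup. The treatment comparison itself is not affected.

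**Working it through.** **1. The plan's own figure.** The documents give no figure for the biomarker model. The stated 80% power belongs to the treatment comparison. For a paired comparison with n = 50, an effect of 0.5 SD of the within-child difference and two-sided alpha 0.01, the noncentrality is 0.5 × √50 = 3.54. The noncentral t with 49 df gives power 0.799. The 80% is therefore reproduced as a paired t-test, and it says nothing about selecting biomarkers.

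**2. Responders per candidate.** Assume 20–40% respond: 50 × 0.20 = 10 to 50 × 0.40 = 20 responders. Per candidate that is 5–10 with k = 2, 2–4 with k = 5, 1–2 with k = 10 and 0.5–1 with k = 20.

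**3. Reference calculation.** For k independent null candidates each tested at level α, P(at least one false predictor) = 1 − (1 − α)^k.

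| k | α = 0.05 | α = 0.01 |
|---|---|---|
| 2 | 1 − 0.95² = 9.8% | 1 − 0.99² = 2.0% |
| 5 | 22.6% | 4.9% |
| 10 | 40.1% | 9.6% |
| 20 | 64.2% | 18.2% |

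**4. Simulated selection, N = 50, no true predictor.** The plan names no algorithm, so two were used.

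- Forward: likelihood-ratio entry, binary markers plus SNPs, 20–40% response. The ranges pool several sets of runs, from a few hundred to 1,500 trials per setting. Part of their width is simulation error: at 45% with 400 trials the standard error is √(0.45 × 0.55/400) = 2.5 points.
- Backward: Wald elimination, independent normal candidates, 30% or 50% response, 2,000 trials per setting (800 for k = 20).

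Percentage of trials keeping at least one false predictor:

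| k | Forward, 0.05 | Backward, 0.05 | Forward, 0.01 | Backward, 0.01 |
|---|---|---|---|---|
| 2 | 9–13 | 7–8 | 2–3 | about 1 or less |
| 5 | 23–29 | 20–21 | 6–8 | about 2 |
| 10 | 43–46 | 37–39 | 10–13 | about 5 |
| 20 | 67–71 | 61–65 | 21–27 | 8–9 |

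With 20 candidates the unpenalised full model failed to converge in about 12–36% of trials.

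**5. Apparent against true discrimination.** In forward-selected null models with 5 to 20 candidates, the AUC in the children used for fitting was 0.68–0.79. In new null children it was 0.50–0.51.

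**6. Effect of fixing k.** Testing each of k named candidates at 0.05/k gives 1 − 0.975² = 4.9% for k = 2, 1 − 0.995¹⁰ = 4.9% for k = 10 and 1 − 0.9975²⁰ = 4.9% for k = 20. When no marker predicts response, Holm has the same chance of a false finding, because its first step uses 0.05/k.

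**The case against.** The strongest reply is that the risk could be small. Aim c names only two marker types, and two candidates at 0.05 give about 7–13%. Aim c is under the Primary Aim, so the 0.01 level might be meant to cover it, and 0.05 appears nowhere in the documents. At 0.01 even 20 candidates give 8–27%. The Tertiary Aim and the optional samples shrink the realistic pool. The synopsis states no stepwise rule, and the forward algorithm used here gives higher rates than the backward one.

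Most of this stands. A reader might infer that the trial will often report chance predictors, or name a subgroup where none exists. The documents do not support that without conditions, because they give neither the number of candidates nor the alpha for this model, and 20 SNPs is no better supported than 3. Nor should the general mention of baseline biomarkers be read as an unlimited pool, since much of it is deferred or optional.

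Two things remain. The 0.01 is attached in the text to multiple primary end-points, and nothing extends it to biomarker selection. And whatever the algorithm, the plan says it will select on significance and provides no correction for having done so.

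**Conclusion.** The concern holds conditionally. The plan states a significance-based selection method for an item of its Primary Aim, in at most 50 children, without fixing the number of candidates, the alpha, a correction or a validation step. Over 2 to 20 candidates, the chance of at least one false predictor runs from about 1% or less (two candidates, backward, 0.01) to 71% (twenty, forward, 0.05). At 0.05 it is a serious risk from about 10 candidates upward (37–71%) and modest with two (7–13%). The apparent AUC of a model selected this way would overstate a true 0.50 by about 0.2 to 0.3.

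The figures assume no true predictor, no dropout, response rates of 20–50% and the two algorithms described. Correlated SNPs would lower them, and dropout would leave fewer than 50 children. What counts as treatment response in this model is itself undefined and must be settled first. This is a cheap improvement, and the treatment comparison is untouched.

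**What to change.** Before unblinding, write into Section 6:

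- the response definition used in the biomarker model;
- FRAA status and a short, named list of SNPs as the only confirmatory candidates, after confirming that both assays will be run, since the Tertiary Aim places folate receptor autoantibodies among deferred work;
- one Firth-penalised logistic model containing all of them, with no selection step. Firth suits this purpose because it copes with sparse data and yields p-values. Ridge and LASSO do not give standard p-values for Holm to adjust, and LASSO itself selects;
- Holm-adjusted p-values at a stated familywise level, and a bootstrap optimism-corrected AUC;
- every other biomarker analysis labelled exploratory.

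The cost is a paragraph of text and a few lines of code, with no new samples, visits or children. The downside is that fewer biomarkers will be called significant.

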15. Clinical Global Impression for Improvement (CGI-I): The CGI-I is a 7-point measure of overall symptomatic change compared to baseline  that will be used as a **key primary** outcome measure. Scores range from 1 (Very Much Improved) through 4 (Unchanged) to 7 (Very Much Worse). All aspects of the child's condition need to be integrated to assign the CGI-I score. The CGI-I will be rated by an assessor who is blind to treatment assignment, AEs, and medication dose. Both the standard CGI-I and the newly developed CGI-I-ASD will be completed, with the CGI-I completed before the CGI-I-ASD. Ratings of Much Improved or Very Much Improved on the CGI-I will be used to define positive response.

16. Parent Target Problems (PTP): At baseline, parents will be asked to nominate the two most important ASD problems for the child. Through brief discussion, the frequency (for episodic behaviors such as insists on daily routines) or constancy (for problems such as language delay or rigidity reflecting more enduring patterns), intensity and impact of the behavior on the family are established. Responses from this systematic inquiry are documented in a brief narrative. The narrative will be reviewed monthly and a new narrative documented. This review will assist with the scoring of the CGI-I in real time.  At the end of the trial, the narratives will be reviewed by a panel blind to treatment assignment. This method has been shown to be reliable and valid in placebo-controlled studies. 

17. Children's Yale-Brown Obsessive-Compulsive Scales-ASD (CYBOCS-ASD): The CYBOCS-ASD is a modified version of the CYBOCS developed for children with Obsessive-Compulsive Disorder.  The modified version is a semi-structured clinician-rated scale designed to rate the current severity of repetitive behavior in children with ASD (i.e., Time Spent, Interference, Distress, Resistance, and Control). Each item is scored from 0 (least symptomatic) to 4 (most symptomatic), yielding a Total score from 0 to 20. It has established reliability and validity  and is sensitive to change. 

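### Primary Aim c specifies no treatment contrast, so the planned logistic biomarker selection can present a marker of general improvement as a predictor of benefit from the supplement

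*Combined protocol and SAP*

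**What the plan says.** Section 4 (Specific Aims) lists under the Primary Aim, as item c: "To determine if specific biomarkers (Folate Receptor Autoantibody, Single Nucleotide Polymorphism) can predict response to treatment". The method appears once, in the Synopsis under Statistical Methods: "Multivariable logistic regression will be used to select biomarkers that can significantly predict treatment response". Section 6 (Statistical Analysis) gives no model for this item and does not mention logistic regression. Its primary model is for another question: "we will use a mixed model using baseline and all post-randomization measures of mitochondrial activity", with no biomarker term stated.

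The predictors are baseline markers. Section 5, Laboratory Assessments, item 8 says: "Baseline biomarkers will help understand whether treatment response can be predicted from biomarker tests".

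The only binary response definition is in Section 5, Developmental Assessments, item 15: "Ratings of Much Improved or Very Much Improved on the CGI-I will be used to define positive response". The same item fixes its reference point: "The CGI-I is a 7-point measure of overall symptomatic change compared to baseline". Nothing links this definition to the logistic model, and no other response definition is given for Aim c.

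A placebo comparison is available for every child. Section 5, Trial Design says: "Each participant will serve as their own control in the cross-over design".

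**The concern.** A child can improve from baseline through placebo response, rater or parent expectation, ongoing therapy or natural change. A regression of improvement status on a marker describes who improves. Aim c asks who improves because of the supplement, and only a comparison with placebo answers that.

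At stake is a claim that an autoantibody or SNP subgroup responds to the supplement when those children would have improved anyway. Section 7 (Importance of the Knowledge To Be Gained) presents finding subgroups who may gain from a supplement as one product of the trial, so the claim would be used.

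**Working it through.** **The plan's own figure.** None is given for Aim c. The stated 80% power belongs to the mitochondrial comparison. It reproduces as 79.9% for a two-sided paired t-test (n = 50, effect 0.5 on the SD of within-child differences, alpha 0.01). It says nothing about Aim c.

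**What each analysis estimates.** Let M be the marker (0/1), g its prognostic effect in both phases, and d the extra effect of the supplement in marker-positive children.

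- Supplement-phase improvement: S = a + gM + t + dM + error
- Placebo-phase improvement: P = a + gM + error
- Marker difference in S: g + d
- Marker difference in S − P: d

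Aim c is about d. A model of S alone returns g + d and cannot separate the two.

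**Simulation inputs.** Taken from the plan: 50 children, each with both treatments. Assumed, because the documents are silent: 50% marker prevalence, within-child correlation 0.5, improvement N(0,1) in each phase, responder if above 0.5, test level 0.05. The response rate is 1 − Φ(0.5) = 31% without the marker and 1 − Φ(0.5 − g) with it.

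**Marker with no predictive value (d = 0): share of trials selecting it**

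| g (SD) | Response, marker − vs + | Supplement-phase logistic | Within-child difference |
|---|---|---|---|
| 0 | 31% vs 31% | about 5–6% | about 5% |
| 0.2 | 31% vs 38% | 10% | about 5% |
| 0.5 | 31% vs 50% | 31% | about 5% |
| 0.8 | 31% vs 62% | 66% | about 5% |
| 1.0 | 31% vs 69% | 82% | about 5% |

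The logistic column is good to several points only. Runs of the same set-up gave 26–32% at 0.5 SD, 58–66% at 0.8 SD and 78–84% at 1.0 SD, varying in part with the logistic test used.

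**Second set of assumptions, as response rates.** With 4,000 trials per setting and rates equal in both phases, supplement-phase logistic regression selects a purely prognostic marker in 35% of trials (20% vs 40%), 64% (20% vs 50%) and 86% (20% vs 60%). The within-child contrast stays at about 5%. If the 20% vs 50% split is instead truly predictive (placebo 20% in both groups), the logistic model again selects it in 64%. The two situations look the same to that model.

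**Power of the contrast for a truly predictive marker.**

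- Binary outcome, 0.8 SD: about 49% with the contrast, 65% with supplement-phase logistic regression. In the response-rate version: 53% vs 64% (20% vs 50%) and 76% vs 85% (20% vs 60%).
- Continuous outcome, 0.8 SD: about 78% with or without the contrast. At correlation 0.5 the variance of S − P is 2(1 − 0.5) = 1, the same as that of S. At correlation 0 the SD would be √2 = 1.41, and the contrast would lose precision.
- Carryover (assumed): if a fraction c of the benefit persists into a following placebo phase, the half of the children who take the supplement first lose cd from their contrast, so its mean is d(1 − c/2). For d = 0.8 this is 0.6 at c = 0.5 and 0.4 at c = 1. Simulated power falls from 78% to 54% and 26%.

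**Selection among several markers.** The number of candidates is not stated. With independent null markers tested at 0.05, the chance of at least one false selection is 1 − 0.95⁵ = 23% for 5 and 1 − 0.95¹⁰ = 40% for 10. At assumed response rates of 20% to 50%, one phase yields 50 × 0.20 = 10 to 50 × 0.50 = 25 responders, which is thin for multivariable selection.

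**The case against.** The strongest reply is that the plan is silent rather than wrong. It names no model terms, no period and no response for Aim c. Items a and b of the same aim are framed against placebo, so a placebo-referenced or mitochondrial response may be intended. This stands in part. A reader might infer that the model is known to omit treatment, but the documents show only that no contrast is specified. It does not remove the point: the one stated method is regression of response on markers, and the one binary response available has no placebo reference.

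Second, nothing in the documents shows that these markers predict 12-week improvement, and 0.8 SD exceeds the 0.5 assumed for treatment. This stands. A reader might infer that false predictors will be reported. The supported statement is that they can be, if a marker is prognostic. An unrelated marker is selected at about the nominal rate.

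Third, a reader might infer that the contrast is free, or that it raises power. It does not. On a binary outcome it loses power. Any gain over the logistic model (about 78% against 65% at 0.8 SD) comes from the continuous outcome. Trial Design also describes no washout, so carryover can dilute the contrast.

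Fourth, the aim could be called exploratory. The text does not call it so: it sits under the Primary Aim, and the Synopsis speaks of significant prediction.

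**Conclusion.** The point holds in this form: for Primary Aim c no treatment contrast and no tied response definition are specified, and the stated method, run as written, cannot separate prognostic from predictive markers. Under the assumed conditions, a marker with no predictive value and a prognostic effect of 0.2 to 1.0 SD is selected in about 10% to 82% of trials, against about 5% with a within-child contrast. The range depends on the assumed prognostic strength, prevalence, correlation and responder threshold, none of which the documents give. The direction does not depend on them, because a supplement-phase model estimates g + d. This is more than missing detail: the cross-over already collects the data for a better analysis. It should be corrected before the data are analysed.

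**What to change.** In Section 6, replace the logistic selection with the following.

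1. Name the response outcome for Aim c, on a continuous scale. If it is mitochondrial activity, the scale must express normalization, because Trial Design admits children both above and below average.
2. List the baseline markers in advance: folate receptor autoantibody status and a short named set of SNPs.
3. Test each marker as a marker-by-treatment interaction in the cross-over mixed model, with treatment, period, sequence and marker main effects and a child-level random effect.
4. Correct for the number of markers tested, and report every interaction with a confidence interval.
5. Keep logistic responder models as description only.
6. Because no washout is described, add a sensitivity analysis of the marker-by-treatment interaction using Phase 1 data only.

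The cost is plan wording; no new data are needed. The downside is imprecision. Interaction estimates from 50 children will have wide intervals, and carryover would weaken the contrast. The Phase 1 analysis compares about 25 children per arm, further split by marker, so it can only check consistency. If the sponsor keeps a binary response, it should accept lower power than the supplement-phase logistic model (about 49% against 65% for an assumed 0.8 SD predictive marker) as the price of answering the question asked.
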